#### **9.4 Collection and Recording of Adverse Events**

Changed from:

During the Adverse Event Reporting Period, the PI will record all adverse events.

Changed to:

During the Adverse Event Reporting Period, the Investigator will record all adverse events.

## **REVISION HISTORY**

Version No.	Effective Date	Summary of Change(s)
1.0	14 Dec 21	New document
1.1	21 Jan 22	Corrected the items weight in Appendix 6.7.1 for question 14.
		Added description in Section 4.11.5 to describe algorithms of handling multiple ECG measurements performed at the same visit: the average of results used for continues variables, the worst result used for categorical variables.
	05 Feb 22	Corrected table number in Section 4.10
	15 Feb 22	Section 4.3.3, for the rule handling multiple records, Added "earliest" to illustrate that if there are multiple records are nearest, the earliest one will be used.
	27 Mar 22	Removed duplicate 'X' in Appendix 6.6
	10 May 22	Corrected the 'contrast' statement to 'estimate' statement for the model based average generation in Section 4.10.3.8 and 4.10.3.9
		Corrected table number in Appendix 6.3
	13 Jul 22	Corrected spelling in Section 3.2.1
	10 Oct 23	Section 4.10.1.5, Examination of Subgroups
		Added subgroup analysis by ethnicity:
		North East Asian verses South East Asian
2.0	16 Oct 23	Finalized for final analysis

## LIST OF ABBREVIATIONS

Abbreviation / Acronym	Definition / Expansion
AE	Adverse event
AECOPD	Acute exacerbation of COPD
ANCOVA	Analysis of covariance
ATC	Anatomical Therapeutic Chemical
AUC	Area Under the Curve
BDR	Blinded Data Review
BDI/TDI	Baseline Dyspnea Index/Transition Dyspnea Index
CBL	Change from Baseline
CI	Confidence Interval
COPD	Chronic Obstructive Pulmonary Disease
CRF	Case report form
CSR	Clinical Study Report
DBP	Diastolic Blood Pressure
ECG	Electrocardiogram
eCRF	electronic Case Report Form
ЕоТ	End of Treatment
FAS	Full analysis set
$FEV_1$	Forced expiratory volume in 1 second
FVC	Forced vital capacity
GOLD	Global Initiative for Obstructive Lung Disease
HR	Heart rate
ICS	Inhaled Corticosteroid
IVRS/IWRS	Interactive Voice Response System/ Interactive Web
	Response System
LABA	Long Acting Beta2 Agonist
LAMA	Long Acting Muscarinic Antagonist
LOCF	Last observation carried forward
LS mean	Least squares mean
MedDRA	Medical Dictionary for Regulatory Activities
MAR	Missing at random
MI	Missing imputation
mMRC	modified Medical Research Council
MMRM	Mixed model repeated measures
MNAR	Missing not at random
OR	Odds Ratio
PP	Per protocol analysis set
PR	Pulse Rate
PRO	Patient Reported Outcome
PI	Preferred term
QIC	QI corrected
QICB	QI corrected (Bazett's correction)
	Q1 corrected (Fridericia's correction)
PK SAF	Puise rate
SAE	Serious adverse event
Effective Date: 26 Nov 10	CONFIDENTIAL Project Document Version No. Project Document Effective Date: Date of last signat

Abbreviation / Acronym	Definition / Expansion
SAP	Statistical Analysis Plan
SBP	Systolic Blood Pressure
SGRQ	Saint George's Respiratory Questionnaire
SOC	System organ class
SS	Safety analysis set
TEAE	Treatment-emergent adverse events
WHODRUG	World Health Organization Drug Dictionary

## **1** INTRODUCTION

This initial statistical analysis plan (SAP) describes the planned summaries and statistical analyses of data for the clinical study REV-3001.

The overall objectives of this study are to confirm the efficacy and safety of revefenacin inhalation solution (175mcg once daily) for the treatment of Chinese subjects with moderate to very severe Chronic Obstructive Pulmonary Disease (COPD).

The analyses described in this SAP are based upon the following study documents:

- Study Protocol, Version 2.0 (July 15, 2020)
- electronic Case Report Form (eCRF), Version 4.0 (January 19, 2022)

## **2** STUDY OBJECTIVES

## 2.1 Primary Objective

The primary objective of the study is to confirm the efficacy of revefenacin inhalation solution 175 mcg administered once daily via nebulization for 12 weeks compared to placebo in a population of Chinese subjects with moderate to very severe COPD.

Note: "Revefenacin inhalation solution 175 mcg" will be referred to as "revefenacin 175 mcg" or "revefenacin" in subsequent sections of the SAP.

## 2.2 Secondary Objectives

The secondary objectives of the study are:

- To confirm the safety of revefenacin 175 mcg administered once daily via nebulization for 12 weeks compared to placebo in a population of Chinese subjects with moderate to very severe COPD.
- To characterize the efficacy of revefenacin 175 mcg on patient reported outcomes compared to placebo in a population of Chinese subjects with moderate to very severe COPD.
- To collect pharmacokinetics (PK) samples for population PK analysis of revefenacin 175 mcg in a population of Chinese subjects with moderate to very severe COPD.

## **3** INVESTIGATIONAL PLAN

#### 3.1 Overall Study Design and Plan

#### 3.1.1 Study Design

This is a randomized, double-blind, placebo-controlled, parallel-group, multi-center study in Chinese subjects with moderate to very severe COPD treated for 12 weeks.

The study population consists of

- Males and females of Chinese ethnicity, at least 40 years of age;
- A clinical diagnosis for at least 6 months prior to screening of COPD according to Global Initiative for Chronic Obstructive Lung Disease (GOLD) guidelines;
- Subjects capable of performing reproducible spirometry maneuvers and with a postipratropium Forced Expiratory Volume in 1 second/Forced Vital Capacity (FEV1/FVC) ratio <0.7 at Screening Visit 2;
- Subjects with moderate to very severe COPD with a post-ipratropium FEV1 <80% of predicted normal FEV1 and an absolute FEV1 > 700 mL at Screening Visit 2;
- Current smoker or ex-smoker, with a history of at least 10 pack-years of tobacco smoking. Ex-smokers must have stopped smoking >6 months prior to Visit 1.

Subjects who are currently using stable doses of long-acting beta-adrenoceptor agonist (LABA)-containing products (LABA monotherapy or inhaled corticosteroid (ICS)/LABA fixed dose combination) will be permitted to enroll into the study and continue to take their LABA or ICS/LABA COPD medication. All other prohibited COPD medications will be required to be stopped. Salbutamol as rescue medication is permitted.

Eligible subjects will be centrally randomized to receive revefenacin 175 mcg or placebo in a 1:1 ratio, stratified by concomitant LABA use (Yes, No) and reversibility to ipratropium (Yes, No).

Each subject will receive treatment once daily in the morning for a total of 12 weeks. The two treatments will both be administered as a 3 mL solution by inhalation using a jet nebulizer. Subjects with a concomitant LABA will dose the LABA or ICS/LABA prior to nebulization.

The schematic of the study design is shown in Figure 1.

#### Statistical Analysis Plan

#### **Figure 1: Study Diagram**

Placebo inhalation solution, once daily (n = 160)

prior medications (eg, 7 days for LAMAs) is not required prior to performing the ipratropium reversibility test at V2

#### 3.1.2 Schedule of Activities

The schedule of study procedures is shown in Table 1.

CONFIDENTIAL

## **Table 1: Schedule of Activities**

VISIT	1 (Screen 1)	2 (Screen 2) 	3 Randomization	4	5	6 (EoT)	Early term (ET)	Follow up (Telephone)
NOMINAL DAY (Allowable Window)	-14 (-30 to -4)	-7 (-10 to -4)	1	29 (22-36)	57 (50-64)	85 (78-92)		7-14 days after V6/ET
NOMINAL WEEK	-2	-1	0	4	8	12		
Written informed consent	X							
IVRS/IWRS transaction	X		X	X	X	X	x	X
Demography and medical history (incl. COPD, smoking, and exacerbation history)	x							
Review concomitant medications	X	X	X	X	X	X	x	X
Physical examination	X					Х	X	
Chest X-ray (if not done in past 12 months)	X							
Height and weight	X							
Vital Signs (supine or semi-recumbent blood pressure, pulse rate)	x		x 			x 	X	
12-lead ECG (supine or semi-recumbent)	X		X 			x 	X	
Spirometry (FEV 1 , FVC) pre-bronchodilator		X						
Spirometry (FEV 1 , FVC) 45 min post-ipratropium (500 mcg nebulized)		X						
Laboratory Safety – Blood and Urinalysis	X					X	x	
Pregnancy Test	X		X	X	X	X	x	
Dispense Rescue Medication (salbutamol pMDI)	x		x	X	x			
Dispense Daily Diary	x		X	Х	х			

CONFIDENTIAL

Project Document Version No. 2.0 Project Document Effective Date: Date of last signature Page 12 of 49

VISIT	1 (Screen 1)	2 (Screen 2) 	3 Randomization	4	5	6 (EoT)	Early term (ET)	Follow up (Telephone)
NOMINAL DAY (Allowable Window)	-14 (-30 to -4)	-7 (-10 to -4)	1	29 (22-36)	57 (50-64)	85 (78-92)		7-14 days after V6/ET
NOMINAL WEEK	-2	-1	0	4	8	12		
Record Adverse Events	X	X	X	X	X	Х	X	X
Medication Training	x 		X					
Pre-dose Spirometry (FEV 1 , FVC), -45 and -15 min pre-dose.			X	X	X	X	X	
Complete BDI/TDI 			X	X	X	X	X	
Complete SGRQ			X			X	X	
Complete mMRC			X					
Randomization			X					
Administer Study Medication in Clinic			X	X	X	Х		
Dispense Outpatient Study Medication			X	X	X			
Post-dose Spirometry (FEV 1 , FVC), 5, 15, and 30 minutes, and 1, 1.5, and 2h			X			X		
PK sampling			x 	x 	x 	x 		
Record Rescue Medication and Study Drug in Diary, Review at Clinic Visits		X	X	X	X	X	X	

1. Visit 2 (Screening Visit 2) can be conducted on the same day as Visit 1 (Screening Visit 1) if the subject does not require washout of other COPD medications (e.g., 14 days for LAMAs) prior to the ipratropium reversibility test at Visit 2.

2. Pre-dose and at approximately 1 hour post-dose.

3. Train subject on rescue medication use.

4. BDI is performed at V3 and TDI is performed at V4, V5, and V6.

Mylan Pharma UK Ltd. REV-3001

5. PK sampling will be performed pre-dose (within 30 minutes of dosing) and at any time 1 - 30 minutes post-dose at Visit 3, 4, 5, and 6. At Visit 6, an additional PK sample will be collected during the sampling interval of 1 - 4 hours post-dose

## 3.1.2.1 Screening

Screening will involve one or two visits, depending on whether a washout period is required for prohibited COPD medications. The assessments for Visit 1 and Visit 2 may be conducted on the same day if a subject does not require washout of COPD medications prior to the spirometry assessments. Hence, initial screening can occur up to 30 days prior to randomization with key spirometry assessments occurring ~4-10 days prior to randomization.

Prior to the ipratropium reversibility testing during screening, short acting bronchodilators must be withheld for  $\geq 6$  hours.

A subject may be re-screened, however, the subject would need to be reconsented and would be assigned a new Subject ID via IWRS.

#### 3.1.2.2 Study Treatment Period

Eligible subjects will be randomized on Day 1 (Visit 3) to double-blind treatment and enter a 12-week placebo-controlled study period where efficacy and safety are planned to be assessed in clinic at Visit 4 (Day 29), Visit 5 (Day 57) and Visit 6 (Day 85).

The first dose of study treatment will be administered on the morning of Day 1/Visit 3 at the study site. Both the start and end times of the administration of study treatment will be captured. Subsequent doses will be self-administered at home by the subject except on days with a scheduled visit to the study site. They will be advised to administer the study drug every morning at approximately the same time within the window of 6 am and 11 am. The time of administration will be recorded by the subjects in their diary.

Spirometry testing will be performed 45 minutes and 15 minutes prior to dosing of study drug at Visits 3-6, and post-dose at 5, 15, 30 minutes and 1, 1.5 and 2 hours after completion of nebulized dose of study drug at V3 and V6 only.

Salbutamol as a rescue medication is permitted but must be withheld for  $\geq 6$  hours before the first spirometry performed at each study visit and whilst serial spirometry is performed to 2 hours post-dose on Day 1 and Day 85. Use of salbutamol as a rescue medication will be documented in a medication diary and recorded in the eCRF.

Unless consent is withdrawn, subjects who prematurely terminate study drug will have an early termination (ET) visit scheduled as soon as possible after their last dose of study drug.

## 3.2 Endpoints

#### **3.2.1 Efficacy Variables**

In the following section, the efficacy endpoints have been defined more precisely than they were in the protocol. Therefore, definitions may differ slightly from the protocol. For example, "Change from baseline" is included in the primary endpoint definition.

- Primary endpoint
  - Change from baseline (CBL) Trough FEV1 on Day 85
- Secondary endpoint

- CBL to Peak FEV1 (0-2h) on Day 1
- Number (%) of St. George's Respiratory Questionnaire (SGRQ) responders (total score ≥4 units) on Day 85
- Transition Dyspnea Index (TDI) focal score on Day 85
- Average count of salbutamol puffs per day (Days 1-85)
- Percentage of salbutamol rescue free 24h periods (Days 1-85)
- CBL Trough FEV1 on Days 29 and 57
- TDI focal score on Days 29 and 57
- CBL in Weighted Mean FEV1 (0-2h) on Days 1 and 85
- CBL to Peak FEV1 (0-2h) on Day 85
- CBL Trough FVC on Days 29, 57 and 85
- CBL SGRQ total score on Day 85
- Number (%) of TDI responders (focal score  $\geq 1$ ) on Days 29, 57 and 85

## 3.2.2 Safety Variables

- Adverse Events (AEs)
- Acute Exacerbation of COPD (AECOPD)
- Laboratory Tests
- Vital Signs (blood pressure and pulse rate)
- 12-lead ECG

## 3.2.3 Pharmacokinetic Variables

Pharmacokinetic (PK) data for Population PK analyses will be collected. The plans for the analysis and reporting of this data are outside the scope of this SAP and will be separately reported.

PK sampling will be performed pre-dose (within 30 minutes of dosing) and at any time 1-30 minutes post-dose at Visit 3, 4, 5, and 6. At Visit 6, an additional PK sample will be collected during the sampling interval of 1-4 hours post-dose.

## 4 STATISTICAL METHODS

## 4.1 Data Quality Assurance

All tables, figures and data listings to be included in the report will be independently checked for consistency, integrity and in accordance with standard procedures.

## 4.2 Randomization and Unblinding Processes

Assignment of Subject Identification number (SID), randomization number and study drug, as well as site drug inventory control will be managed by an automated Interactive Web Response system (IWRS). A manual containing complete instructions for Web access and use will be provided to each site prior to study start. At their first clinic visit, the IWRS will assign a SID. Each SID will be unique and serve as the primary subject identifier throughout

all phases of the study. The SID must appear on all CRF pages, source documents, laboratory data, central spirometry, ECG, diary data, and PRO data. Subjects qualifying to enter the drug treatment phase, will be assigned an additional "randomization number" by the IWRS at randomization. Subjects will be allocated to treatment within blocks for the given allocation ratio.

At Visit 3 (Day 1 of dosing), eligible subjects will be randomized to receive revefenacin 175mg or matching placebo in a 1:1 ratio through the IWRS. The randomization will be stratified according to the subject's concomitant LABA use (Yes, No) and reversibility to ipratropium (Yes, No).

Emergency subject unblinding will be managed by an automated IWRS. A manual containing complete instructions for Web or telephone access and use will be provided to each site prior to study start.

Subjects may be allowed to continue on the study drug after emergency unblinding if the subject does not meet the criteria for study drug termination and/or withdrawal from the study or were accidentally unblinded not due to the reason of safety. These subjects will be considered as protocol deviations and excluded from the relevant analysis populations.

## 4.3 General Presentation Considerations

## 4.3.1 Treatment Arms and Labels

In tables, figures and listings, the following treatment labels or abbreviations will be used, depending on the column space available:

- Revefenacin 175 mcg; Placebo
- REV 175 mcg; Placebo

#### 4.3.2 Definitions and Derivations

#### **Baseline Assessments**

Unless otherwise specified in Section 4.6, baseline is defined as the last non-missing observation before the first dose of study drug. Both date and time will be included in the comparison for the determination of baseline. For assessments that are required to be done on the date of first dose and pre-dose, but the time of the assessment is not collected, the last non-missing observation on the date of first dose will be considered as baseline assessment.

#### Reversibility

Reversibility to ipratropium is defined as post-bronchodilator  $FEV_1$  change of  $\geq 12\%$  and  $\geq 200$  mL relative to the pre-bronchodilator  $FEV_1$ . Reversibility (Yes, No) is captured directly in the CRF as part of the randomization information.

#### GOLD Categories

GOLD 2019 Severity of Airflow Limitation Categories (GOLD 1-4) and GOLD 2019 categories (GOLD A-D) are defined in Table 2 and Table 3 below.

GOLD 1-4 will be derived from the percent predicted  $FEV_1$  (%) collected at screening Visit 2. The modified Medical Research Council Dyspnea Scale (mMRC) captures the description of breathlessness on a 0-4 scale and will be collected in the CRF and reported. GOLD A-D will be as collected on the CRF at screening as part of COPD History.

GOLD airflow category	Severity	FEV 1 threshold
GOLD 1	Mild	$\geq$ 80% predicted
GOLD 2	Moderate	$\geq$ 50%, <80% predicted
GOLD 3	Severe	$\geq$ 30%, < 50% predicted
GOLD 4	Very severe	< 30% predicted

Table 2: GOLD Severity of Airflow Limitation Categories

## Table 3: GOLD 2019 Categories

Moderate or Severe Exacerbation History	Assessment of Symptoms / Risk of Exacerbations		
$\geq 2$ or $\geq 1$ leading to hospital admission	С	D	
0 or 1 (not leading to	Α	В	
hospital admission)	mMRC 0-1	mMRC ≥2	
	Symp	otoms	

## COPD Duration (years)

COPD duration is calculated as (date of informed consent – date of first diagnosis of COPD +  $1) \div 365.25$ .

In case of missing or partial diagnosis date, the imputation rules below will be applied:

- If day is missing and the month and year are available, the diagnosis date is imputed as the mid day of the month (eg 15th).
- If day and month are missing and only a year is available, the diagnosis date is imputed as the mid day of the year (eg 1st July).
- If both month and year are missing, no imputation will be done.

#### The number of years smoked

As per the CRF completion guidelines, years of smoking is derived from only the YEAR component of a date. For ex-smoker, calculated as year stopped smoking – year started smoking; for current smoker, calculated as year of informed consent – year started smoking.

#### Study Day

When study day is used, the following algorithm will be used:

• study day = date of assessment – date of first dose of study medication + 1, if the date of the assessment is on or after the date of first dose;

• study day = date of assessment – date of first dose of study medication, if the date of the assessment is prior to the date of first dose.

## 4.3.3 Analysis Windows

The summary tables will only include the assessments at scheduled visits, except the spirometry measurements. Unscheduled assessments will be included in the listings.

Unscheduled spirometry measurements with study medication taken on the same day will be mapped to corresponding visit and timepoint according to Table 4 and Table 5. Unscheduled spirometry measurements with no study medication taken on the same day will not be mapped. Spirometry measurements at an early termination visit will be mapped to the schedule visit according to Table 4.

If multiple visits fall within a window, the earliest visit with acceptable spirometry data nearest to the scheduled day will be included in the analysis.

Visit (Day) in Protocol	Analysis Visit	Target Study Day	Visit Window
Visit 3 (1)	Day 1 (Baseline)	1	1
Visit 4 (29±7)	Day 29	29	$2 \leq$ Study Day $\leq 43$
Visit 5 (57±7)	Day 57	57	$44 \leq \text{Study Day} \leq 71$
Visit 6 (85±7)	Day 85	85	$72 \leq $ Study Day

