### 6.2.5 Early Study Drug Termination (ET) Visit

Subjects may request termination of study drug or withdrawal from the study at any time, or be required to withdraw or terminate study drug by the Investigator or Sponsor for reasons as per Section 4.2.4. If study drug is terminated or the subject withdraws or is withdrawn, the reason for termination/withdrawal should be established and recorded. If a subject does not

return for a scheduled visit, every effort should be made to contact the subject. In any circumstance, every effort should be made to document the outcome of subject contact attempt, if possible. The Investigator will contact Mylan or designee in the event that a subject fails to complete the study or violates the protocol.

If the subject withdraws from the study and also withdraws consent for disclosure of future information, no further evaluations should be performed and no additional data should be collected. The Sponsor may retain and continue to use any data collected before such withdrawal of consent.

Unless consent is withdrawn, subjects who prematurely terminate study drug will be asked to return to the clinic for an ET visit and will have this scheduled as soon as possible after their last dose of study drug.

At the ET visit the following procedures will be completed:

- Complete the following questionnaires in this sequence: TDI, SGRQ.
- Record vital signs – supine or semi-recumbent blood pressure and pulse rate.
- Record 12-lead ECG – supine or semi-recumbent (single measurement). ECG must be performed prior to spirometry and blood sampling.
- Urine or serum pregnancy test (if female of child-bearing potential).
- Blood and urine will be collected for safety laboratory tests.
- General physical examination, including respiratory, cardiovascular, gastrointestinal, musculoskeletal, neurological systems, lymph nodes, skin, extremities, head, ears, eyes, nose, and thyroid gland.
- Review and record concomitant medications.
- Collect and review rescue medication use recorded in daily diary.
- Two spirometry (FEV1, FVC) assessments corresponding to -45 and -15 minutes pre-dose assessments at previous visits.
- Assess and record AEs.

Subjects may be discharged from the clinic at the discretion of the Investigator following completion of all ET assessments.

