#### 4.11.4 Clinical Laboratory Evaluation

Clinical laboratory tests will be performed at times defined in the study schedule. Any clinically significant changes in laboratory safety data should be recorded as an AE.

Hematology, chemistry and urinalysis will be collected. Laboratory data will be summarized in terms of observed values and changes from baseline and will be tabulated at each scheduled time point by treatment group and overall.

Hematology, chemistry and urinalysis data will be presented in tables as changes from baseline relative to normal ranges (e.g. shifts from normal to abnormal).

All hematology, serum chemistry and urinalysis data will be listed with values flagged if outside of the normal range.

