## Electrocardiogram

Twelve-lead ECG measurements will be measured from a single recording at screening and pre-dose and at 1 hour post-dose on Day 1 and 85.

Baseline and change from baseline for QT, QTcF, HR, QRS, RR and PR will be summarized using descriptive statistics by treatment group and visit.

For QTcF a classification of absolute values and increases from baseline will be performed. The number of subjects with maximum absolute QTcF <450 msec, 450 msec  $\leq$ QTcF <480 msec, 480 msec  $\leq$ QTcF <500 msec and QTcF values  $\geq$ 500 msec will be tabulated by treatment and visit. The number of subjects with maximum increase from baseline QTcF <30 msec, 30 msec  $\leq$ QTcF <60 msec and QTcF  $\geq$ 60 msec will be tabulated by treatment and visit.

when multiple assessments of ECG taken at a post-baseline timepoint, for the continues variables, the average of results at the same timepoint will be used, for the categorical variables, the worst ECG finding at that timepoint will be used.

All recorded values for the ECG parameters will be listed by subject. A separate listing of subjects with values of QTcF  $\geq$ 500 msec or an increase  $\geq$ 60 msec will be provided, as necessary.

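### Unscheduled safety results are kept out of the summary tables, and early-termination laboratory, ECG and vital-sign results have no stated place in them

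*SAP*

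**What the plan says.** SAP 4.3.3 gives the general rule: "The summary tables will only include the assessments at scheduled visits, except the spirometry measurements". The next sentence deals with the remainder: "Unscheduled assessments will be included in the listings". ET data are mentioned there for one kind of measurement only: "Spirometry measurements at an early termination visit will be mapped to the schedule visit according to Table 4".

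The safety sections follow the same pattern.

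- Laboratory (SAP 4.11.4): results "will be tabulated at each scheduled time point by treatment group and overall", with a further table of shifts relative to the normal range.
- ECG (SAP 4.11.5): "Twelve-lead ECG measurements will be measured from a single recording at screening and pre-dose and at 1 hour post-dose on Day 1 and 85". ET is not named. QTcF is then categorised by its maximum absolute value and by its maximum rise; the second table begins "The number of subjects with maximum increase from baseline QTcF <30 msec". Both are tabulated by treatment and visit.
- Vital signs (SAP 4.11.5): screening, Day 1 and Day 85 are named, with descriptive and change-from-baseline summaries.

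The protocol does collect safety data at ET. Section 6.2.5 lists vital signs and a 12-lead ECG, and adds: "Blood and urine will be collected for safety laboratory tests". SAP 4.3.4 sets the percentage denominator as the number of subjects in the analysis set, not the number with data.

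**The concern.** Subjects who stop treatment early are a selected group. Protocol 4.2.4 requires study drug to stop after a moderate or severe exacerbation and allows it to stop for an adverse event. For these subjects the ET visit may hold the last, and for laboratory tests the only, planned post-dose safety result.

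If that result is not tabulated, the subject stays in the denominator of a laboratory shift table with no chance of entering the numerator. The percentage then errs low, and by different amounts in the two arms if stopping differs between them. A QTcF table headed as a maximum likewise omits any higher value recorded off schedule or at ET.

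Confirming safety is a secondary objective, and SAP 4.11 plans no formal treatment comparison for safety. The descriptive tables therefore carry much of the safety evidence.

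**Working it through.** **Which results does the rule reach?**

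1. *Unscheduled results.* Exclusion of laboratory, ECG and vital-sign values from the tables is express in SAP 4.3.3.
2. *ET results.* Exclusion is inferred. The inference rests on four things:
   - The spirometry sentence treats ET as something to be mapped onto a scheduled visit, and gives that mapping for spirometry alone.
   - SAP 4.11.5 names only screening, Day 1 and Day 85 for ECG and vital signs.
   - SAP 4.11.4 tabulates laboratory data by scheduled time point.
   - Where the SAP wants ET data used elsewhere, it says so, as for SGRQ in 4.10.3.4 and 4.10.3.5.
3. *Repeat ECGs at one post-baseline timepoint.* These are used: averaged for continuous variables, worst finding for categorical ones. That provision does not extend to ECGs at ET or at unplanned times.

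**What is left for a subject who stops before Visit 6, if ET is not tabulated?** In the Schedule of Activities (Protocol Table 1-1, SAP Table 1), laboratory tests fall at Visit 1, Visit 6 and ET. ECG and vital signs fall at Visit 1, Visit 3, Visit 6 and ET. Such a subject has no post-baseline laboratory value in the tables, and after dosing only the one-hour Day 1 ECG and vital signs. (The protocol synopsis instead places ECG and vital signs at every visit from 3 to 6. I follow the schedule tables, Protocol 6.2.2 and 6.2.3, and SAP 4.11.5. The choice does not affect the laboratory point.)

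**How many subjects?** Inputs from SAP 4.12: 256 evaluable, 20% dropout, 320 randomized, ceiling of 428.

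- The plan's own figure reproduces: 256 / (1 − 0.20) = 320.
- Upper bound at 320: 0.20 × 320 = 64, or 32 per arm if split equally.
- Upper bound at the ceiling: 0.20 × 428 = 85.6, about 86.
- If fewer stop (assumed range 5% to 10%): 0.05 × 320 = 16; 0.10 × 320 = 32.

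**Effect on a shift percentage.** Let d be the fraction stopping early, and assume that all of them attend ET and that the true shift rate p is the same in stoppers and completers.

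- Tabulated without ET: (1 − d) × p.
- With ET included: (1 − d) × p + d × p = p.
- Ratio: 1 − d, which is 0.80, 0.90 and 0.95 for d = 0.20, 0.10 and 0.05.

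The shortfall is smaller if some stoppers miss ET, and larger if stoppers have the higher shift rate.

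**The case against.** The strongest reply is that ET counts as scheduled. It has its own column in both schedules, and SAP 3.1.2.2 says that subjects who stop early "will have an early termination (ET) visit scheduled as soon as possible after their last dose of study drug". SAP 4.3.3 contrasts scheduled with unscheduled and does not place ET among the unscheduled. The mapping rule may be confined to spirometry simply because spirometry must be assigned to Day 29, 57 or 85 to enter the repeated-measures model, whereas safety data could sit in an ET row without mapping. This stands as far as it goes: the exclusion of ET results is not stated. But neither is any such row, and unscheduled values are excluded on either reading.

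Four further points are correct and limit the finding.

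- A reader might infer that shift and maximum tables for vital signs and ECG all lose data. No shift or maximum table is planned for vital signs, and no shift table for ECG. The shift point concerns laboratory tests and the maximum point QTcF; vital signs are affected only in their by-visit summaries.
- Maximum QTcF is tabulated by visit, so it can be read as a within-visit maximum and not a study-wide one. On that reading the table is not mislabelled, but no table then shows the highest value a subject reached.
- A reader might infer that early stoppers vanish from the safety tables. They remain in the Safety Set. Clinically significant laboratory, vital-sign and ECG changes are to be recorded as adverse events, and those arising up to 30 days after the last dose are tabulated, with separate tables for events leading to discontinuation.
- All values are listed. QTcF of at least 500 msec, or a rise of at least 60 msec, has its own listing as necessary. That listing does not cover the 450 to below 500 msec and 30 to below 60 msec bands, and no listing corrects a tabulated count.

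Protocol 7.5.3.3 also calls for changes that lead to out-of-range laboratory values to be both listed and summarized, with no visit limit in that sentence. SAP 4.13 does not record a narrowing.

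**Conclusion.** The concern holds in a limited form. Unscheduled safety results are expressly kept out of the summary tables. ET laboratory, ECG and vital-sign results have no defined place in them and, on the natural reading, are omitted. With the denominator in SAP 4.3.4, laboratory shift percentages can be understated, as can QTcF category counts.

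The ET part affects at most about 64 of 320 subjects (about 86 of 428). That bound assumes that the full 20% planning allowance is realised, that every stopper attends ET, and that ET is treated as off schedule. The true number will be lower: subjects who withdraw consent or are lost to follow-up supply no ET data. If ET counts as scheduled, only unscheduled results are affected. The documents do not support saying that 64 subjects' collected safety data will be missing, or that the data are lost. The primary efficacy analysis is untouched.

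**What to change.** In SAP 4.3.3 or 4.11:

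1. Add a worst post-baseline row, drawing on scheduled, unscheduled and ET results, to the QTcF absolute-value and increase category tables and to the laboratory shift tables.
2. Show ET laboratory, ECG and vital-sign values as their own row or column in the by-visit summaries.

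The data are already collected. The cost is a sentence or two in the SAP and one row or column per table. The worst-value row mixes assessment times, so it should be labelled as such and kept separate from the by-visit rows. SAP 4.13 calls for changes after version 2.0 is finalized to be documented in the clinical study report; this one can be recorded there.
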